7.1. Study Subjects

7.1.1. Disposition of Subjects

Subject disposition will be summarized in a CONSORT flow diagram similar to Figure 1. The number of subjects in each box of the figure will be reported, including the final number analyzed for the primary objective in each randomization arm. The reasons for subjects being removed from the primary objective analysis set will be reported in the flow diagram.

7.1.2. Clinical Investigation Plan Deviations

Deviations from the CIP are collected on an electronic Case Report Form (eCRF). A summary table of deviations will be reported using the Medtronic coding captured on the Medtronic Use Only eCRF. A listing of all deviations with typical and relevant details will be reported.

7.1.3. Analysis Sets

Cut-off dates will be applied to the study data when creating snapshots for study reporting. The analysis sets will be created from the applicable snapshot (e.g., for final report).

Enrolled

Patients who signed informed consent and met inclusion/exclusion criteria. Deviations and adverse events will be reported for all enrolled subjects. Enrolled subjects will be included in the CONSORT flow diagram.

Randomized

Enrolled subjects who are randomized.

Modified intent-to-treat

A modified intention-to-treat (mITT) analysis will be performed for the primary objectives. The mITT analysis set will include all randomized subjects that undergo a pulmonary vein isolation procedure (i.e. have a cryocatheter inserted). Patients that are randomized, but exit the study without undergoing a pulmonary vein isolation procedure will not be included in the mITT analysis set. Patients that are randomized to the treatment arm, but do not have the renal denervation procedure, will not be included in the mITT analysis set.

This analysis set is used for the following objectives described previously in Section 4:

- Primary safety

- Primary effectiveness
- Ancillary Objective 1
- Ancillary Objective 2
- Ancillary Objective 3
- Ancillary Objective 4
- Ancillary Objective 6

Secondary Objective

All subjects in the mITT cohort (i.e. subjects used for the Primary Effectiveness Objective) that do not undergo an additional pulmonary vein ablation procedure during the 90 day blanked follow-up period will be included the analysis of the secondary objective.

Ancillary Objective 5

The following subjects will be included in the analysis of ancillary objective 5:

- All subjects in the mITT cohort (i.e. subjects used for the Primary Effectiveness Objective) that do not undergo an additional pulmonary vein ablation procedure during the 90 day blanked follow-up period will be included this analysis

AND

- Have not used Class I and III anti-arrhythmic drugs following the blanking period

Case Report Form (CRF) data will be used to determine if subjects have or have not used Class I and III anti-arrhythmic drugs following the blanking period. If a subject has not used Class I anti-arrhythmic drugs and has not used Class III anti-arrhythmic drugs at all following the blanking period, then they will be used for this analysis. If a subject has used either Class I or Class III anti-arrhythmic drugs after the blanking period, then they will be excluded from this analysis.

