## 6.8 Enrollment and baseline

When a patient signs and dates the Consent Form, he/she is considered a subject enrolled in the study. The date the subject signed the Consent Form and Authorization to Use and Disclose Personal Health Information/Research Authorization must be documented. The following evaluations will be performed after consent, unless previously performed as part of routine clinical evaluations within the specified windows:

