### 12.2 General considerations

A modified intention-to-treat analysis will be performed and will serve as the primary analysis for all objectives in this study. The modified intention-to-treat

cohort will include all randomized subjects that undergo a pulmonary vein isolation procedure (i.e. have a cryocatheter inserted). Patients that are randomized, and meet either of the following two conditions will not be included in this cohort:

- exit the study without undergoing a pulmonary vein isolation procedure
- subjects who are randomized to the treatment group and are found not to meet inclusion/exclusion criteria during the renal denervation procedure.

The Statistical Analysis Plan (SAP) will include a comprehensive description of the statistical methods and reports to be included in the final study report. Any change to the data analysis methods described in the CIP will require an amendment only if it changes a principal feature of the protocol. Any other change to the data analysis methods described in the protocol, and the justification for making the change, will be described in the clinical study report.

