7.10.1.5. Datasets Analyzed

The mITT analysis set will be used for this objective.

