7.11. Safety Evaluation

A summary table of AEs by classification the following classifications will be reported:

- Serious Adverse Events (SAE)
- Unanticipated Adverse Device Effects (UADE)
- Complication or observation
- Procedure relatedness
- System relatedness

A second table will be reported summarizing AEs by MedDRA preferred term.

The tables will show the counts of the number of a specified AE classification (e.g., SAE, MedDRA term, etc.) and the number of subjects who experienced the specified AE classification, and calculate the percentage of subjects who experience the specified AE classification.

A listing of all AEs will be reported with one row per AE.

All AEs for the enrolled analysis set will be included. The CEC classification of AEs will be used, except for SAEs and UADEs, where the Medtronic classification will be used since those are not adjudicated by the CEC.

Example summary table (the final validated version may differ)

Number of Events (Number, % Subjects)	Subjects Not Randomized (N = N _S)	Subjects Randomized (N = N _S)	Subjects Enrolled (N = N _S)
Total Adverse Events	177 (116, 35.3%)	177 (116, 36.4%)	177 (116, 36.4%)
Serious Adverse Event			
Yes	97 (66, 20.1%)	97 (66, 20.7%)	97 (66, 20.7%)
No	80 (64, 19.5%)	80 (64, 20.1%)	80 (64, 20.1%)
Unanticipated Adverse Device Effect			
Yes	0 (0, 0.0%)	0 (0, 0.0%)	0 (0, 0.0%)
No	177 (116, 35.3%)	177 (116, 36.4%)	177 (116, 36.4%)
Complication or Observation			
Complication	0 (0, 0.0%)	0 (0, 0.0%)	0 (0, 0.0%)
Observation	177 (116, 35.3%)	177 (116, 36.4%)	177 (116, 36.4%)
Procedure Relatedness			
Related	49 (43, 13.1%)	49 (43, 13.5%)	49 (43, 13.5%)
Cryoablation	49 (43, 13.1%)	49 (43, 13.5%)	49 (43, 13.5%)
Repeat cryoablation	0 (0, 0.0%)	0 (0, 0.0%)	0 (0, 0.0%)
Renal angiogram	N _E (N _S , % _S)	N _E (N _S , % _S)	N _E (N _S , % _S)
Renal CT	N _E (N _S , % _S)	N _E (N _S , % _S)	N _E (N _S , % _S)
Renal denervation	N _E (N _S , % _S)	N _E (N _S , % _S)	N _E (N _S , % _S)
Reveal LINQ	N _E (N _S , % _S)	N _E (N _S , % _S)	N _E (N _S , % _S)
Other	N _E (N _S , % _S)	N _E (N _S , % _S)	N _E (N _S , % _S)
Not Related	126 (83, 25.2%)	126 (83, 26.0%)	126 (83, 26.0%)
Unknown	2 (2, 0.6%)	2 (2, 0.6%)	2 (2, 0.6%)

Number of Events (Number, % Subjects)	Subjects Not Randomized (N = Ns)	Subjects Randomized (N = Ns)	Subjects Enrolled (N = Ns)
Cryoablation	49 (43, 13.1%)	49 (43, 13.5%)	49 (43, 13.5%)
Repeat cryoablation	0 (0, 0.0%)	0 (0, 0.0%)	0 (0, 0.0%)

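### The SAP's Enrolled set adds an eligibility condition that the protocol does not have, so adverse events in consented subjects who fail a criterion drop out of the AE tables as written

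*SAP*

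**What the plan says.** The two documents define enrolment differently.

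- Protocol 6.8: "When a patient signs and dates the Consent Form, he/she is considered a subject enrolled in the study". No eligibility condition is attached. Protocol 9.2.1 starts AE collection at the same signature, for serious, cardiovascular, procedure-related and system-related events.
- SAP 7.1.3, Enrolled: "Patients who signed informed consent and met inclusion/exclusion criteria". This adds a second condition.

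The SAP set then governs reporting. SAP 7.1.3 states "Deviations and adverse events will be reported for all enrolled subjects", and SAP 7.11 states for its tables and listing "All AEs for the enrolled analysis set will be included". The Randomized set is nested inside it: "Enrolled subjects who are randomized".

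The primary safety objective uses a different population. SAP 7.10.1.5 states "The mITT analysis set will be used for this objective". Protocol 12.2 removes from the modified intention-to-treat (mITT) cohort "subjects who are randomized to the treatment group and are found not to meet inclusion/exclusion criteria during the renal denervation procedure". The SAP's own rule in 7.1.3 is broader: "Patients that are randomized to the treatment arm, but do not have the renal denervation procedure, will not be included". I found no safety set in the SAP made up of everyone who had a study procedure started.

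**The concern.** A programmer builds analysis sets from the section that defines them. Built from SAP 7.1.3, the Enrolled set leaves out consented subjects who fail a criterion, although the protocol counts them as enrolled and collects their AEs. Protocol 1.2 expects a fair number of such failures. The same set governs deviations, so subjects taken in against the criteria are the ones who would leave the deviation summary.

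The more important group is small. Renal angiography is done only in the Treatment arm and only after PVI (protocol 6.9 and 6.12). A Treatment subject found ineligible at that point has already been exposed to PVI and to an arterial angiogram. That subject is outside mITT, so a vascular complication, which is a component of the primary safety composite (protocol 12.3), would not count there. If the subject is also outside Enrolled, the AE tables would not show the event either. Control subjects have no angiogram and cannot be excluded by this route.

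**Working it through.** The plan gives no figure for this point. The check compares set membership, followed by one subtraction.

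**Step 1. Who is in which output, reading SAP 7.1.3, 7.10.1.5 and 7.11 literally**

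| Subject | Enrolled, protocol 6.8 | Enrolled, SAP 7.1.3 (AE tables) | mITT (primary safety) |
|---|---|---|---|
| Consented, fails blood pressure or CT anatomy, not randomised | Yes | No | No |
| Consented, eligible, withdraws before randomisation | Yes | Yes | No |
| Control, had PVI, later found not to have met a criterion | Yes | No, if judged in hindsight | Yes |
| Treatment, had PVI, found ineligible at angiography | Yes | Depends on when eligibility is judged | No |
| Treatment, had PVI, eligible, no denervation for another reason | Yes | Yes | No under the SAP rule |

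The first row is a definite loss under the stated rule. The fourth row turns on timing.

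**Step 2. When is eligibility judged?** SAP 7.1.3 does not say.

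- *Pointing to before randomisation:* protocol 6.8 and 6.9 and SAP 5.3 place randomisation after CT has confirmed renal anatomy. SAP section 6 describes the later exclusions as randomised subjects. Since Randomized is nested in Enrolled, that description keeps them in the AE tables.
- *Pointing to angiography:* protocol 6.12 says angiography is done to confirm anatomy and restates anatomic eligibility there. The fibromuscular dysplasia exclusion (protocol 5.2.2) is defined by its angiographic appearance. Protocol 12.1 and 12.2 and SAP section 6 all say these subjects fail the inclusion/exclusion criteria, which is the negation of the SAP's Enrolled condition.

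Both readings are available from the text.

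**Step 3. Is the SAP consistent with itself?** It is not. SAP 5.1 allows up to 245 enrolled because many will fail screening. SAP 5.3 tells sites to exit enrolled subjects who are not randomised. SAP section 6 lists blood pressure and renal anatomy failures among enrolled subjects who are not randomised. The example AE table in SAP 7.11 has a Not Randomized column beside the Enrolled column. All of these use the consent sense or fit it. Under 7.1.3 the Not Randomized column could hold only eligible subjects who were not randomised.

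**Step 4. Size.** Inputs: up to 245 consented and 70 randomised (protocol 1.2, SAP 5.1).

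- 245 − 70 = 175
- 175 / 245 = 71.4%

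This is a ceiling. It assumes all 245 places are used, and it includes elective withdrawals (protocol 12.1, SAP section 6), who need not have failed any criterion. The documents do not give the share failing on eligibility, so the range is 0 to 175. The number of Treatment subjects found ineligible after PVI is not given either. Those subjects do not count toward the 70, so at exactly 245 consents each one would take one from the 175.

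**The case against.** The strongest reply is that this is a drafting slip with little practical effect. The SAP's other uses of the word and the Not Randomized column suggest that a consent-based set was intended. On the SAP's own nesting, Treatment subjects excluded after PVI are randomised, hence Enrolled, hence in the AE tables. AE capture is not in doubt: events are collected from consent, the events committee reviews deaths and AEs (SAP 5.5), and the monitoring committee sees accumulating safety data (protocol 12.8).

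Much of this stands. It limits the claim to reporting and makes the loss of the post-PVI subjects from the AE tables one reading among two. It does not remove the contradiction: the governing definition says something else, and two programmers could produce different AE denominators.

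A reader might infer more than the documents support:

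- *That these events appear in no safety table.* This is too broad. A Control subject who had PVI and proved ineligible stays in mITT and so in primary safety. Part of SAP 7.11 was also not in the text available for this check.
- *That 71% of subjects lose their AE reporting.* That figure is the ceiling in Step 4 for all non-randomised subjects.
- *That each post-PVI exclusion is 1 in 35 (2.9%) of the Treatment arm.* These subjects are additional to the roughly 35 counted in that arm, so the denominator is wrong.
- *That the CONSORT diagram hides them.* SAP 7.1.1 requires reasons for removal from the primary analysis set to be shown there. SAP 7.1.2 also promises a listing of all deviations without naming a population.
- *That the AE table comparison between arms is biased.* The visible example table has no arm columns.

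**Conclusion.** Wrong as written. The SAP's Enrolled definition contradicts protocol 6.8 and the SAP's own usage. Followed literally, it removes from the AE tables and listing the events of consented subjects who fail a criterion.

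For Treatment subjects found ineligible at angiography after PVI, exclusion from primary safety is explicit. Exclusion from the AE tables is possible but not certain, because the SAP does not fix the time at which eligibility is judged.

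The size cannot be stated beyond 0 to 175 non-randomised subjects at the planned ceiling, plus an unstated number of post-PVI exclusions. The finding rests on reading SAP 7.1.3 as the operative definition for 7.11, which is what 7.11 says. Power, alpha and the primary effectiveness analysis are not affected by this point.

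**What to change.** In SAP 7.1.3, define Enrolled as all subjects who signed the consent form, citing protocol 6.8. In SAP 7.11, state that every subject in whom a study catheter was inserted is included in the AE tables by assigned arm, whether or not later found ineligible, and that Treatment subjects found ineligible after PVI are shown separately.

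The cost is one or two sentences, plus arm columns in the example table. No new data are needed, because AEs are already collected from consent. Reported AE counts may rise slightly. The change does not return the post-PVI exclusions to the primary safety analysis; that depends on the mITT definition, which is a separate question.

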## 6.10 Pulmonary vein isolation procedure

Perform the pulmonary vein isolation procedure first using Arctic Front Advance/Arctic Front Advance Pro. Investigator is to perform the procedure according to the procedural steps in this protocol and the Instructions for Use for the Arctic Front Advance/Arctic Front Advance Pro Cardiac Cryoablation System. Appropriate systemic anticoagulation and sedation should be attained at the investigators discretion according to their institutions pre- established procedures/guidelines at the time of the procedure. Current recommendations for anticoagulation are found in the 2012 Expert Consensus Statement on the Ablation of atrial fibrillation.

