5.6. Data Monitoring Committee

A DMC will periodically review accumulating safety data for the study, including the rate of safety composite events within each study arm and the difference in the rate between study arms (i.e., the Primary Safety Objective).

6. Determination of Sample Size

The overall study sample size is 70 randomized subjects that undergo a pulmonary vein isolation procedure which is the required sample size for the primary effectiveness objective.

Subjects that are enrolled in the study may not go on to be randomized due to a variety of reasons, including elective withdrawal prior to randomization, blood pressure measurements that do not meet study criteria, or renal anatomy that is found to be ineligible upon angiography. Based on the rate of randomization among enrolled subjects in trials with similar screening criteria, up to 245 subjects may need to be enrolled and undergo screening in order to ensure that 70 subjects are randomized.

There will be at least 78% power to test the primary effectiveness objective provided at least 70 subjects undergo randomization and undergo a pulmonary vein isolation procedure. Table 1 below shows the expected incremental power at each analysis. The first and second look correspond to the interim analyses. The third interim look is the final analysis.

Table 1: Power at each stage of the analyses

Look	Patients w/ six month follow-up	Expected Incremental Power of Analysis
1	32	17.6%
2	50	10.1%
3	70	50.9%
Cumulative Power:		78.6%

Subjects who are randomized and meet either of the following two conditions do not count toward the 70 randomized subjects to be used in the mITT set (define below):

- Exit the study without undergoing a pulmonary vein isolation procedure
- Subjects who are randomized to the treatment group and are found not to meet inclusion/exclusion criteria during the renal denervation procedure

The sample size calculation is based on the following assumptions:

- 1:1 randomization
- Constant randomization rate over 16 months
- Last enrolled subject followed through 6 months post-procedure
- 50% chronic treatment success in the Control arm (PVI only) versus 75% in the Treatment arm (equivalent to a hazard ratio of 0.415) through 6 months post-procedure
- Constant hazard ratio over all follow-up
- Constant attrition (dropout) of 5% per 6 months

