7.10.1.2. Performance Criteria and Rationale

Given the exploratory nature of a feasibility study, there is no performance requirement for this objective. The rate of safety composite endpoints will be characterized by estimating the rate within each arm and estimating the difference in rates between arms. These event rate estimates will provide critical guidance for designing a possible subsequent pivotal study.

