7.10.1.3. Endpoint Definition

The primary safety composite endpoint combines the safety endpoints from current Medtronic hypertension and AF studies and is intended to include serious adverse events associated with either the renal artery denervation or cryoablation procedure.

The endpoint for this objective is a Safety Composite Event. Safety Composite Events are events that are serious, occur within a specified time interval (see Table 11) starting when the subject undergoes the study pulmonary vein isolation procedure and meet the definition in Section 12.3.1. The CEC

adjudication will be used to classify subjects for this endpoint. The adjudication source is the Medtronic Adverse Event CRF, Section C, question 1. The date of Safety Composite Events will come from the Adverse Event CRF.

Table 1. Safety Composite Events and onset intervals

Serious Adverse Event	Onset Interval
Death	1 month
End-stage renal disease	1 month
Significant embolic event	1 month
Renal artery perforation requiring intervention	1 month
Renal artery dissection requiring intervention	1 month
Vascular complications	1 month
Hospitalization for hypertensive crisis	1 month
New renal artery stenosis	6 months
Cardiac damage	1 month
Pulmonary vein stenosis	6 months
Atrio-esophageal fistula	6 months
Arrhythmia	1 month
Persistent phrenic nerve palsy	6 months

Serious Adverse Event Definitions

- Death
- End-stage renal disease defined as two or more eGFR measurements <15mL/min/1.73m² at least 21 days apart and requiring dialysis for one or more of the following: volume management refractory to diuretics, hyperkalemia unmanageable by diet and diuretics, acidosis bicarbonate <18 unmanageable with HCO₃ supplements, or symptoms of uremia, nausea, vomiting.

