7.13. Changes to Planned Analysis

Any change to the data analysis methods described in the CIP will require an amendment only if it changes a principal feature of the protocol. Any other change to the data analysis methods described in the CIP or this SAP, and the justification for making the change, will be described in the clinical study report.

The CIP states 'all randomized subjects will be included in the analysis' of some objectives (e.g., CIP section 12.4.5). This differs from CIP section 12.2 that states the mITT analysis set will serve as the primary analysis for all study objectives. The analysis sets for each objective as stated in this SAP will be used for the final report analyses.

8. Validation Requirements

Minimum validation requirements for the programs written to execute the analyses in this SAP:

- Primary objectives: Level I (independent program)
- Secondary objective: Level II (peer review)
- Ancillary objectives: Level II (peer review)

- AE tables and listings: Level II (peer review)
- Deviation table and listing: Level II (peer review)
- CONSORT diagram numbers: Level II (peer review)
- Other programs needed for final report analyses not specified: Level II (peer review)

Programs previously validated at Level I or Level II further modified with minor changes may be validated at Level III.

It is expected that Standard Operating Procedures will be followed for other programs that effect the programs written to execute the analyses in this SAP, such as data retrieval programs, dataset mapping programs, analysis dataset programs, etc.

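### SAP 7.1.3 drops every Treatment subject not denervated from mITT, while the CIP and SAP 6 drop only those found ineligible during denervation

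*SAP*

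**What the plan says.** All versions of the rule leave out randomised subjects who exit without PVI. They differ on a second exclusion, which applies to the Treatment arm only.

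- **SAP 7.1.3** (the SAP's only definition of the set): "Patients that are randomized to the treatment arm, but do not have the renal denervation procedure, will not be included in the mITT" set. No reason for the missing denervation is required.
- **CIP 12.2** (the primary analysis cohort for all objectives) leaves out "subjects who are randomized to the treatment group and are found not to meet inclusion/exclusion criteria during the renal denervation procedure". CIP 12.1 uses the same condition to decide who counts toward the 70.
- **SAP 6** repeats the CIP condition, "Subjects who are randomized to the treatment group and are found not to meet inclusion/exclusion criteria during the renal denervation procedure", for those who "do not count toward the 70 randomized subjects to be used in the mITT set (define below"). The definition that follows in 7.1.3 is a different one.
- **SAP 7.13**: "The analysis sets for each objective as stated in this SAP will be used for the final report analyses". The CIP conflict it describes is all randomised subjects versus mITT. It does not mention the difference described here.

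SAP 7.10.1.5 and 7.10.2.5 use this set for primary safety and primary effectiveness. On the order of events, CIP 6.10 says "Perform the pulmonary vein isolation procedure first using Arctic Front Advance/Arctic Front Advance Pro", and SAP 7.10.1.3 counts safety events "starting when the subject undergoes the study pulmonary vein isolation procedure". Renal angiography follows PVI, in Treatment only (CIP 6.12), and CIP Table 8 lists it apart from denervation.

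**The concern.** Under 7.1.3, whether a Treatment subject is analysed can depend on what happened during PVI, after the safety clock has started. A PVI complication that leads the team not to proceed to denervation would remove both the subject and the event from the Treatment rate. The same complication in Control stays in, because Control has no second procedure to miss. Read literally, an angiography complication that prevents denervation would also leave the Treatment rate, although renal artery dissection requiring intervention is a listed component of the composite.

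The primary safety rates are meant to inform the design of a pivotal study (SAP 7.10.1.2). SAP 7.10.1.4 also allows the arms to be called significantly different if the interval for the difference excludes 0. An exclusion that can only lower the Treatment rate for PVI events works against both uses.

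There is a bookkeeping problem as well. A subject not denervated for a reason other than ineligibility counts toward the 70 under SAP 6 but is not analysed under 7.1.3. With k such subjects, the analysed set is 70 - k.

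**Working it through.** **1. The rules applied to the possible cases**

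| Subject | CIP 12.1/12.2 and SAP 6 | SAP 7.1.3 |
|---|---|---|
| Either arm, exits without PVI | out | out |
| Treatment, PVI done, found ineligible during denervation, not denervated | out | out |
| Treatment, PVI done, not denervated for another reason | in, and counts toward the 70 | out |
| Treatment, denervation started, then found ineligible | out | may be in |
| Control, PVI done, PVI complication | in | in |

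The third row is the main conflict. The fourth shows that the rules are not strictly nested: 7.1.3 does not say whether having the procedure means that it was started or completed.

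**2. The plan's own power figure**

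Inputs from SAP 6: looks at 14, 19 and 41 events; boundaries 2.576, 2.611 and 2.049; hazard ratio ln(0.75)/ln(0.5) = 0.415. The mean of the log-rank Z at d events is sqrt(d/4) x |ln 0.415|, with |ln 0.415| = 0.879. This gives 1.65, 1.92 and 2.82. The incremental crossing probabilities are 17.6%, 10.1% and 50.9%, total 78.6%, as in SAP Table 1. The design figures are not in dispute; they serve below to price the fix.

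**3. Safety: effect of one removed event**

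Assume 35 subjects per arm (70 at 1:1). Exact (Clopper-Pearson) 95% intervals for Treatment:

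- 1/35 = 2.9% (0.1-14.9%) becomes 0/34 = 0% (0-10.3%).
- 2/35 = 5.7% (0.7-19.2%) becomes 1/34 = 2.9% (0.1-15.3%).

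**4. Safety: how likely this is**

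CIP 12.3.4 gives a composite rate of 3.1% for cryoablation in the STOP-AF trial. The share r of those events that is recognised before denervation and stops it is not in the documents, so r = 5% to 25% is assumed.

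- Chance of at least one removed event in 35: 1 - (1 - 0.031r)^35. For r = 0.05, 1 - (0.99845)^35 = 5.3%. For r = 0.10, 10.3%. For r = 0.25, 1 - (0.99225)^35 = 23.8%.
- Expected understatement of the Treatment rate: 3.1% x r = 0.16, 0.31 and 0.78 percentage points. Allowing for the smaller denominator, it is 0.15, 0.30 and 0.76.

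**5. What keeping such subjects costs in power**

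A simulation used 35 per arm, 16-month accrual, a 22-month study, 5% dropout per 6 months and the final boundary of 2.049 alone. An assumed number k of Treatment subjects are not denervated and carry the Control hazard. Simulation error is about 0.5 points.

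| k | Kept (CIP 12.2) | Dropped (SAP 7.1.3) |
|---|---|---|
| 0 | 77% | 77% |
| 1 | 76% | 78% |
| 3 | 69% | 76% |
| 5 | 65% | 73% |

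**The case against.** The strongest reply has four parts.

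*The governing rule is identified.* A reader might infer that the documents leave it open which rule applies. They do not quite do so. SAP 6 is about counting and defers the definition of the set; 7.1.3 is the only definition in the SAP; 7.13 says the SAP's sets will be used. This stands. What remains is a departure from CIP 12.2 that is neither mentioned nor justified, and a counting rule that does not match the analysed set.

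*The mechanism is hypothetical and the effect small.* No passage describes a PVI complication stopping denervation or says how often it would. On the assumption above, 76-95% of trials lose no event. The expected understatement is under one point, against an exact interval about 15 points wide for 1/35. The objective is descriptive: "Given the exploratory nature of a feasibility study, there is no performance requirement for this objective". All of this stands and limits the weight of the point. It is no reason to keep an exclusion that works in one direction only.

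*Safeguards exist.* The CONSORT diagram gives reasons for removal (SAP 7.1.1), adverse events are reported for all enrolled subjects (SAP 7.11), the DMC reviews composite rates by arm (SAP 5.6), and SAP section 3 does not limit further analyses. Such events would therefore be visible. But the example adverse event table is split by randomisation status, not by arm, and the tipping-point analysis in SAP 7.4 changes only censored subjects, not excluded ones. In the text available, no specified analysis restores the event to the comparison by arm. Part of the SAP after the adverse event tables was not available, so this is not a claim about the whole document.

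*The supplementary analysis goes beyond the wording error.* This is partly right. Aligning the sentence cures the contradiction. The extra analysis addresses a feature that CIP 12.2 shares: it too excludes after PVI, in Treatment only.

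**Conclusion.** The point holds as an unexplained departure of SAP 7.1.3 from CIP 12.1 and 12.2 that also conflicts with SAP 6. It should be fixed, because the set serves both primary objectives and 7.1.3 as written can take PVI or angiography complications out of the Treatment safety rate. The illustrated size is 1/35 to 0/34 if one event is lost, a 5-24% chance of losing at least one, and an expected understatement of 0.2-0.8 percentage points. These figures rest on 35 per arm, the 3.1% rate carrying over to this population, and an assumed 5-25% of events stopping denervation.

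Two stronger readings are tempting and are not supported.

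- A reader might infer that the exclusion inflates the false-positive rate for effectiveness. That needs removed subjects to have a different AF prognosis, which the documents do not show. It would also need far more removals than the safety illustration implies: 3.1% x 5-25% is below 1% of the arm. No error-rate figure is claimed.
- A reader might blame the exclusion for the planned log-log interval failing when Treatment has no events. That interval is undefined at zero events under either definition. At a 3.1% rate, 0/35 has a chance of (0.969)^35 = 33% with nobody removed.

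**What to change.** Replace the second exclusion in SAP 7.1.3 with the CIP 12.2 condition, so that CIP 12.1, CIP 12.2, SAP 6 and SAP 7.1.3 define one mITT set. This also removes the question of what having the procedure means, because exclusion then turns on an eligibility finding and not on whether denervation took place.

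Add one pre-specified supplementary analysis of primary safety in all randomised subjects with a cryocatheter inserted, by assigned arm. The same for primary effectiveness is optional. Label any analysis restricted to subjects who had denervation as a sensitivity analysis.

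The cost is a SAP amendment; the CIP text can stay as it is. Keeping undenervated Treatment subjects in the primary set costs some power if there are any: at the final look about 76% against 78% with one such subject, and 69% against 76% with three (numbers assumed). In the supplementary analysis, subjects found ineligible may exit early, as CIP 6.24 permits, and would be censored then.
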